7.4.7 Unscheduled Visit

The Investigator has the option of bringing a study subject back in for an unscheduled visit during the treatment period for safety reasons [e.g., study subject complaint of moderate to severe ocular symptom(s), an AE]. An unscheduled visit CRF should be completed. At minimum, the Investigator should record the following:

- a. Investigator evaluation of ocular pain

NOTE: The Investigator that interviewed and record the subject's response to ocular pain at Visit 4 (Day 1 post-op) should interview the subject at this visit

- b. Inspection of the masked punctal plug via the slit lamp, if applicable
- c. Monocular Distance Visual Acuity (Uncorrected)
- d. Slit-Lamp examination

NOTE: The Investigator that slit-lamp evaluation at Visit 4 (Day 1 post-op) should perform the slit-lamp evaluation at this visit.

- e. Recording of any reported adverse event(s).
- f. Concomitant medication

Any changes, discontinuation or addition of an open-label medication(s) must be recorded on the Concomitant Medication CRF.

Table 1: Schedule of Assessments, Events

EXAM PARAMETERS	v1	v2	v3	v4	v5	v6	v7
Inform Consent/HIPPA	①						
Demographic data/Medical Hx/Medication Use	① A						
Concomitant Medication	①	②	③	④	⑤	⑥	⑦
Urine Pregnancy Test (if applicable)	① B						
Subject Randomization to Treatment		②					
Investigator Evaluation of Ocular Pain	① C	②		④ F	⑤ F	⑥ F	⑦ F
Uncorrected Distance VA	① C				⑤	⑥	⑦
Manifest Refraction	① C					⑥	⑦
Best-Corrected Distance VA	① C					⑥	⑦
Slit Lamp Examination	① C			④ F	⑤ F	⑥ F	⑦ F
Insertion of Masked Punctal Plug		②					
Inspection of Masked Punctal Plug		② D	③ E	④ D	⑤ D	⑥ D	⑦ D
Evaluation of lower puncta	①						
Pupil Measurements			③ G				
Type and Grade Cataract	①						
Monocular Cataract Extraction/IOL Implantation			③				
Fundus Examination	①						⑦
Removal of Masked Punctal Plug							⑦ H
Adverse Event Recording		②	③	④	⑤	⑥	⑦

Keys to Abbreviations:

- A = Prior 12 months
- B = Pregnancy test (women of childbearing potential)
- C = Evaluation of Both Eyes
- D = Evaluation using slit-lamp
- E = Visual inspection after surgery
- F = Investigator that performs the slit-lamp and/or ocular pain evaluation at Visit 4 (Day 1 post-op) should perform ALL post-op visit evaluations
- G = Measurement to occur prior to surgery and immediately after surgery
- H = All masked punctal plugs must be removed at the subject last visit

Visit Schedule:

- v1 = Day -30 to -1
- v2 = 1 to 2 days prior to surgery
- v3 = Surgery Day
- v4 = 1 day post-op
- v5 = 3 ± 1 days post-op
- v6 = 7 ± 1 days post-op
- v7 = 14 ± 2 days post-op

7.5 Emergency Anaphylactic or Overdose Procedures, Dose Modification

Dose modification of the study drug/device is not required in this study.

NOTE: Use caution when administering nepafenac to a subject who has previously exhibited sensitivities to phenylacetic acid derivatives and salicylate hypersensitivity as the potential for cross-sensitivity exists. This study is not expected to cause AEs different in type or intensity from those previously reported in published clinical research literature regarding the use of topical nepafenac (NEVANAC® or ILEVRO®). Refer to the Investigator Brochure and [Appendices 4 and 5](#) for additional information.

Should a subject experience a significant medical issue, the subject may be treated according to the Investigator's medical judgment. Any changes, discontinuation or addition of a post-op medication(s) must be recorded on the Concomitant Medication CRF.

7.6 Concomitant Medications

7.6.1 Pre-Study Concomitant Medication Use

Pre-study concomitant medications are defined as all prescription and over-the-counter medications taken within 30 days (whether continuing or not) prior to Visit 3 (Day 0). All prior medications must be documented on the Concomitant Medications CRF.

7.6.2 Concomitant Medication Use

Each study subject will be instructed not to use any other ocular drops, gels or ointments in his or her eyes that have not been prescribed by the Investigator. Systemic medications being used at Visit 1 that are permitted by the study protocol (see inclusion/exclusion criteria for details), are considered necessary for the study subject's welfare, and will not interfere with the study may be used.

All prescription systemic, ophthalmic and over-the-counter concomitant medications used concurrently (from Day -30 to Day 14), that are considered necessary for the study subject's welfare, and will not interfere with the study, may be used but must be documented on the Concomitant Medication CRF. The use of all concomitant medications during the study, including all pre -, intra- and post-operative medications, including intravenous solutions, dilating drops, irrigations, viscoelastics, antimicrobials/ anti-infectives, miotics, etc. related to the surgery, will be documented. The medication name, start and stop dates, indication, dose, route of administration and any dosing alterations must be documented on the Concomitant Medications CRF through completion of the last study visit.

In case of intolerable irritation due to standard post-op open-label medication(s) prescribed by their Investigator, a study subject is to notify the Investigator immediately. If necessary, the open-label treatment regimen may be temporarily altered, or the treatment may be stopped and appropriate therapy administered at the Investigator's discretion. Any changes, discontinuation

or addition of an open-label medication(s) must be recorded on the Concomitant Medication CRF.

7.7 Prohibited Medications, Treatments and Procedures

7.7.1 Prohibited Medications

The use of any systemic, topical and/or ophthalmic NSAID or corticosteroid within 48 hours of Visit 2 or during the course of the study (Visit 2 to Visit 7) is not allowed unless medically necessary. If an NSAID, corticosteroid or an immunosuppressant is required for any condition (ocular or systemic), the study subject will be terminated from the study, have their masked punctal plug removed and will be followed through Visit 7 (Day 14) or if required until the condition has resolved or has become medically stable.

Investigational/experimental/off-label usages of drugs or devices are not permitted during the study, except as described in the protocol.

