5.5.1.1 Reason for Termination

A study subject will be terminated from the study if in the Investigators medical judgment, it was in the best interest of the study subject that developed or reported: a) moderate to severe signs or symptoms of ocular inflammation or pain, b) reported a serious AEs, regardless of relation to the study drug/device or has died.

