5.5.1.2 Reason for Discontinued

A study subject will be discontinued from the study if the Investigator is unable to insert a punctal plug in to the study subject's lower punctum, they have experienced a complication (intra-operative exclusion criteria) during surgery, the punctal plug has been extruded after the surgical visit (Visit3), study subject has used a prohibited concomitant therapy, is non-compliant, has missed scheduled study visits, has personal reasons, has relocated out of the area or has a desired to withdraw from further participation in the study in the absence of a medical need as determined by the Investigator. Other reason – the study subject was discontinued for a reason other than those listed above, the Investigator must specify the reason

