7.9 Rescue Medications

During the study some patients, as determined by the investigator, may require additional rescue medications in the study eye due to post-op ocular pain and/or inflammation the patient is experiencing. Rescue treatment will be allowed per pre-specified rescue criteria ([Section 7.9.1](#)); if the rescue criteria are not met, the medications will be considered prohibited medications. Prohibited medications, though discouraged, could be used but would be considered protocol deviations.

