7.9.1 Administration of a Rescue Medication

Following cataract surgery, a rescue treatment with an ocular topical corticosteroid (prednisolone acetate 1% q.i.d.) should be administered in the study eye, at the discretion of the physician, if any of the following rescue criteria apply:

- a. Anterior Chamber Cell grade is 3 (grade 3 = 16-30+ cells) or greater
- b. Anterior Chamber Flare grade is 3 (grade 3 = moderate intensity) or greater
- c. Subject reports moderate to severe ocular pain

A study subject will be followed through Visit 7 (Day 14) or until the study subject's post-op ocular pain and/or inflammation in the study eye has resolved or has become medically stable. The use of a rescue medication during the study will be documented on the Concomitant Medication CRF.

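### No single rule covers an eye that needs a corticosteroid: 7.7.1 ends participation and removes the plug with no rescue exception, 7.9 and 7.9.1 allow rescue without settling plug or study status, and post-rescue readings have no scoring rule

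*Combined protocol and SAP*

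**What the plan says.** **Prohibited medications (7.7.1).** NSAIDs and corticosteroids are barred from 48 hours before Visit 2 through Visit 7 unless medically necessary. The section then says: "If an NSAID, corticosteroid or an immunosuppressant is required for any condition (ocular or systemic), the study subject will be terminated from the study". The plug comes out and follow-up runs through Day 14, or longer if needed. There is no exception for rescue and no pointer to 7.9.

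**Rescue (7.9, 7.9.1).** Rescue is allowed when the criteria are met: cell grade 3 or more, flare grade 3 or more, or moderate to severe pain. Then "a rescue treatment with an ocular topical corticosteroid (prednisolone acetate 1% q.i.d.) should be administered in the study eye", at the physician's discretion. On follow-up: "A study subject will be followed through Visit 7 (Day 14) or until" pain or inflammation has resolved or is medically stable. Neither section mentions the plug, termination or replacement. Outside the criteria, 7.9 says "if the rescue criteria are not met, the medications will be considered prohibited medications", and adds: "Prohibited medications, though discouraged, could be used but would be considered protocol deviations".

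**Exit rules (5.5).** On the investigator's judgment, 5.5.1.1 permits termination for "moderate to severe signs or symptoms of ocular inflammation or pain". Section 5.5.1.2 discontinues a subject when the "study subject has used a prohibited concomitant therapy". Terminated subjects are not replaced (5.5.2.1); discontinued subjects are (5.5.2.2).

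**Analysis (10).** Section 10.1 lets subjects or visits be excluded for major violations and names prohibited medication as an example. Section 10.4.2 keeps all ITT data and places exclusions in the per-protocol set. Section 10.4.3 bases efficacy on observed data. Rescue appears only as a safety variable (10.4.4).

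**The concern.** A rescue dose of prednisolone is a corticosteroid required for an ocular condition, so it meets the literal trigger in 7.7.1. A site that reads 7.7.1 removes the plug and exits the subject. A site that reads 7.9.1 may give the steroid and leave the plug in place. Each can say it followed the protocol.

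Three things are at stake.

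- **Exposure.** If the plug stays, an N-PPDS eye receives an NSAID and a topical steroid together. Both appended labels (Appendices 4 and 5, section 5.2) caution that this may increase healing problems.
- **Who is counted.** An eye that needs a steroid for pain or inflammation is a likely treatment failure. If it is discontinued and replaced, the failure leaves the completed set and a fresh subject takes its place.
- **What is measured.** Pain is the primary variable at Days 1, 3, 7 and 14. Readings after rescue reflect the steroid, with or without the plug, and the plan does not say how to score them.

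**Working it through.** The plan states no rescue rate, power or sample size calculation, so there is no figure to reproduce. The check is a comparison of the text, followed by one illustration.

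**1. Steroid given within the rescue criteria.**

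| Section | Study status | Plug | Follow-up |
|---|---|---|---|
| 7.7.1 | Terminated | Removed | Through Day 14, or longer if needed |
| 7.9 / 7.9.1 | Not stated | Not stated | Through Day 14, or until resolved or stable |
| 5.5.1.1 with 5.5.2.1 | May be terminated, on judgment | Removed if terminated | Through Day 14, or until resolved or stable (5.5) |

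Follow-up is not in dispute. Plug and study status are.

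**2. Steroid given by the investigator outside the criteria.**

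| Section | Study status | Replaced? |
|---|---|---|
| 7.7.1 with 5.5.2.1 | Terminated | No |
| 5.5.1.2 with 5.5.2.2 | Discontinued | Yes |
| 7.9 | Deviation recorded; no exit stated | Not stated |

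The first two rows give opposite replacement outcomes for the same eye. Section 4.2 counts 75 subjects evaluated at Visit 7 or terminated, so the label also decides whether the eye counts towards the 75.

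**3. Analysis.** Called prohibited, the steroid is a named ground for exclusion under 10.1. Called rescue, it is not. Under 10.4.2 the ITT data stay in either way. Under 10.4.3 a reading on prednisolone enters as observed.

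**4. Illustration only.** Inputs: 50 N-PPDS and 25 placebo eyes (section 4.1). Day 14 pain-free rates of 85% and 42% are the midpoints of the 84–86% and 38–46% quoted in 2.1 for nepafenac 0.3% drops and vehicle. Assumed: these rates count rescued eyes as failures; half of the non-pain-free eyes are rescued; 80% of rescued eyes are pain-free on steroid.

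- Pain-free: 0.85 × 50 = 42.5 and 0.42 × 25 = 10.5. Not pain-free: 7.5 and 14.5.
- Rescued: 0.5 × 7.5 = 3.75 and 0.5 × 14.5 = 7.25, 11 eyes in all.
- Rescue as failure: 85 − 42 = 43 points.
- Rescued eyes excluded: 42.5/46.25 − 10.5/17.75 = 91.9% − 59.2% = 32.7 points.
- Kept as observed: (42.5 + 0.8 × 3.75)/50 − (10.5 + 0.8 × 7.25)/25 = 91.0% − 65.2% = 25.8 points.

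With 25–75% rescued and 50–100% steroid response, excluded minus kept runs from about −5 points (75% rescued, 50% response: 21.4 − 26.9) to about +12 (60% rescued, 100% response: 29.0 − 17.2).

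**The case against.** The best reply is that nothing here is a head-on contradiction for in-criteria rescue. Section 7.9.1 is silent on the plug; it does not order it kept. A site can give prednisolone, terminate and remove the plug under 7.7.1, follow to Day 14, and satisfy every section. Alternatively, 7.9 can be read as carving rescue out of 7.7.1. A reader might infer two opposing commands, and the text does not support that. What stands is that both readings are open, they lead to different handling, and 7.7.1 states no exception.

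For steroid outside the criteria, recording a deviation does not rule out exit. One could also reserve 7.7.1 for medically required use and 5.5.1.2 for other use. That narrows the conflict but does not remove it: a steroid that the investigator judges necessary, in an eye below the thresholds, falls under both.

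A reader might also infer that the site alone decides whether the eye stays in the analysis. It does not. Section 10.6.3 has every subject and visit assessed before lock and unmasking, 10.1 says only that exclusion may occur, and 10.4.2 keeps all ITT data. But that assessment is given no rule for rescue.

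The illustration is open to fair criticism. It draws rescued eyes only from those with pain, although two of the three criteria are cells and flare. The documents do not say that the quoted rates treat rescue as failure. The excluded-minus-kept gap changes sign, so no direction of bias between those two options is shown. Randomization is stratified by center, so differing site practice falls on both arms.

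**Conclusion.** The concern holds as an inconsistency in the operative text that should be corrected. In-criteria rescue lacks a plug and status rule that agrees with 7.7.1. Off-criteria steroid has incompatible handling, with opposite replacement outcomes. Post-rescue readings have no scoring rule. These conclusions rest on the wording alone and need no assumed rate.

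The size of the effect on the pain result cannot be estimated from the documents. The 43, 33 and 26 points show only that the choice of handling can matter; they depend on assumed rescue and response rates. The effect on pain of plug in versus plug out cannot be estimated at all. On safety, the labels support a caution about NSAID plus steroid. A reader might take this as a contraindication, and the labels do not say that. The study is a pilot with no formal sample size, so the point does not invalidate it.

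**What to change.** 1. **7.7.1 and 7.9.1: state one rule for rescue in both places.** The default, in line with 7.7.1, is that when rescue steroid starts the plug is removed (no sooner than 24 hours after insertion, as 6.1.9 advises), the subject is terminated and not replaced, and all scheduled assessments continue through Visit 7. A written rescue exception in 7.7.1 that keeps the plug would also resolve the conflict, but it accepts NSAID plus steroid in the same eye.
2. **7.9: replace the last sentence.** An NSAID, corticosteroid or immunosuppressant given outside the criteria is handled as in 7.7.1 and is also recorded as a deviation.
3. **5.5.1.2: except these three drug classes** from the prohibited-therapy reason and refer to 7.7.1, so that these subjects are not replaced.
4. **10.1 and 10.4.2: add a rescue rule.** Steroid rescue is not a ground for exclusion from ITT. From rescue onward the eye counts as not pain-free in the No Pain/Pain comparison (10.4.9). Observed post-rescue scores are kept, flagged and shown as a sensitivity analysis.

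The cost is a few short edits. Pain, plug inspection and concomitant medication are already recorded at scheduled and unscheduled visits, so no new visit or test is needed. The downside of the default is that study drug ends at rescue: later readings in those eyes are off the plug, and a symptomatic N-PPDS eye loses any benefit of the NSAID.

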7.7.2 Prohibited Procedures

The following procedures are prohibited during the study period:

- a. An LRI or AI procedure before, during or after cataract surgery
- b. A blepharoplasty before or after cataract surgery
- c. Nd:YAG capsulotomy (e.g., for PCO)

7.8 Prophylactic Medications

The pre- and post-operative use of antimicrobial/anti-infective and the cohesive and dispersive viscoelastics use during surgery will be used at the discretion of the Surgeon/Investigator. The use of Miochol at the conclusion of cataract surgery is recommended but can be avoided at the discretion of the Surgeon/Investigator. The use of any of the above mentioned medications will be documented on the Concomitant Medication CRF.

7.9 Rescue Medications

During the study some patients, as determined by the investigator, may require additional rescue medications in the study eye due to post-op ocular pain and/or inflammation the patient is experiencing. Rescue treatment will be allowed per pre-specified rescue criteria ([Section 7.9.1](#)); if the rescue criteria are not met, the medications will be considered prohibited medications. Prohibited medications, though discouraged, could be used but would be considered protocol deviations.

7.9.1 Administration of a Rescue Medication

Following cataract surgery, a rescue treatment with an ocular topical corticosteroid (prednisolone acetate 1% q.i.d.) should be administered in the study eye, at the discretion of the physician, if any of the following rescue criteria apply:

- a. Anterior Chamber Cell grade is 3 (grade 3 = 16-30+ cells) or greater
- b. Anterior Chamber Flare grade is 3 (grade 3 = moderate intensity) or greater
- c. Subject reports moderate to severe ocular pain

A study subject will be followed through Visit 7 (Day 14) or until the study subject's post-op ocular pain and/or inflammation in the study eye has resolved or has become medically stable. The use of a rescue medication during the study will be documented on the Concomitant Medication CRF.

8 ASSESSMENT OF SAFETY

8.1 Safety Variables

Safety variable for this study include any reported AE after screening, visual acuity, slit lamp biomicroscopy finding, fundus examination findings, use of concomitant and/or rescue medications. To optimize consistency of AE reporting across centers, the study subject will be asked a standard question to elicit any AEs. At each study visit or telephone evaluation of the study subject, study personnel will ask the following question:

"Have you had any problems since your last visit?"

8.2 Definitions

8.2.1 Adverse Event

Adverse Event (AE): any unanticipated sign (including a clinically significant abnormal laboratory finding), symptom, or disease temporally associated with the administration of a medicinal product, whether or not considered related to the investigational product or device.

Medical conditions or diseases present before a subject starts study treatment are only considered AEs if they worsen after the subject starts study treatment.

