2.3 Potential Risks and Benefits

2.3.1 Known Potential Risks

A study subject randomized to receive N-PPDS may have unforeseen risk and could exhibit moderate to severe post-op inflammation and/or ocular pain. However, the risk associated with using N-PPDS to deliver a sustain release of Nepafenac are anticipated to be similar, if not less than, those of commercially available topical 0.1% and 0.3% ophthalmic suspension

of Nepafenac and silicone punctal plug products. In ocular surgery clinical studies with Nevanac®, adverse reactions that occurred in 5-15% of study patients included capsular opacity, decreased visual acuity, foreign body sensation, increase intraocular pressure, and sticky sensation. Adverse reactions that occurred in 1-5% of study patients included conjunctival edema, corneal edema, dry eye, lid margin crusting, ocular discomfort, ocular hyperemia, ocular pain, ocular pruritus, photophobia, tearing and vitreous detachment. Some of these reactions may have been the consequence of the surgical procedure. A summary of known potential risks to humans of topical 0.1% and 0.3% ophthalmic suspension of Nepafenac can be found in the NEVANAC® and ILEVRO® prescribing information (see [Appendices 4 and 5](#)).

A study subject randomized to receive a placebo Punctal Plug Delivery System (p-PPDS) could exhibit moderate to severe post-op inflammation and/or ocular pain. Other risks associated with using a p-PPDS are anticipated to be similar to commercially available punctal plugs use in humans. A study subject could experience ocular discomfort, epiphora, loss of plug, ocular inflammation, and subconjunctival hemorrhage. Less common, but serious, side effects are pyogenic granuloma, damage to the muscle at the opening of the punctum, canaliculitis, or migration of the plug into the canaliculus requiring irrigation or surgery.

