8.6.4 Anticipated Adverse Events

The following is a list including, but not limited to, ocular adverse events that are anticipated. Any event that is unlikely but anticipated must have an adverse event form completed and reported to Mati Therapeutics Inc. (see [Section 8.7](#) for reporting details).

- Endophthalmitis/Intraocular infection
- Hypopyon
- IOL dislocation

- Cystoid macular edema
- Pupillary block
- Retinal detachment/tear
- Corneal edema
- Iritis
- Raised IOP requiring treatment
- Visual symptoms requiring lens removal
- Tilt and decentration requiring repositioning
- Residual refractive error resulting in a secondary intervention

NOTE: Wound burps during the first week postoperatively and suture removal are not considered adverse events for this study.

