8.7 Reporting Procedures

Adverse events that occur from Visit 2 (1-2 days pre-op) through completion of the end-of-study visit must be documented. The Investigator will assess the AE severity and relationship of the AE to the study drug/device. The Investigator will follow the progress of the study subject until the AE either resolves or becomes medically stable. Treatments and medications required to treat AEs must be recorded.

All adverse events, regardless of severity and whether or not attributed to the drug or drug delivery device, are to be reported to Mati Therapeutics Inc. Adverse events are also to be reported to the site IRB per the IRB's reporting requirements.

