10.4.4 Safety Analyses

All study subjects who are exposed or deemed exposed to study medication will be evaluable for safety analysis. A subject is deemed exposed to study medication if they discontinue the study prior to surgery visit and were implanted with a masked PPDS.

The safety endpoints in this study are adverse events, visual acuity, slit-lamp parameters (Lid, conjunctiva, cornea), fundus findings, and use of rescue medication. Safety variables will be summarized using descriptive statistics.

The type, severity, duration and frequency of reported adverse events will be tabulated for each treatment group, by visit. Adverse events will also be summarized for events and a comparison of the proportion of study patients reporting adverse events between groups will be made using a chi-square test. Additionally, any adverse event experienced by a subject after signing informed consent and before exposure will be presented separately in the safety analysis.

Adverse events will be coded using the Medical Dictionary for Regulatory Activities (MedDRA). Treatment emergent AEs (those occurring after insertion of a study PPDS) will be summarized descriptively: The number and percentage of study subjects who experienced an AE and the total number of AEs will be summarized by system organ class and preferred term. Associated AEs, defined as AEs suspected to be treatment related by the investigator, SAEs and serious associated AEs will also be summarized, if necessary. Summaries of each type of event will be prepared by severity and for all severities combined.

Concomitant medication recorded and used during the study will be coded using the World Health Organization Drug Dictionary and listed by subject. Ocular concomitant medications will be identified by each eye in the listing.

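### Section 8.2.1 limits adverse events to unanticipated ones, which contradicts Sections 7.5, 8.6.4, 8.7.3 and 10.4.4 and leaves the recording of common expected reactions to each site's reading

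*Combined protocol and SAP*

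**What the plan says.** The only definition of an AE is in Section 8.2.1: "any unanticipated sign (including a clinically significant abnormal laboratory finding), symptom, or disease temporally associated with the administration of a medicinal product". Its closing words remove any limit on causality. They do not remove the limit on expectedness.

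Three other rules use the term:

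- Section 8.7 on reporting: "All adverse events, regardless of severity and whether or not attributed to the drug or drug delivery device, are to be reported" to the sponsor.
- Section 8.6.4 introduces its list with "The following is a list including, but not limited to, ocular adverse events that are anticipated", and then says "Any event that is unlikely but anticipated must have an adverse event form completed".
- Section 10.4.4 tabulates AEs by arm and adds that a "comparison of the proportion of study patients reporting adverse events between groups will be made using a chi-square test".

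Section 2.3.1 names reactions foreseen with the plug: "A study subject could experience ocular discomfort, epiphora, loss of plug, ocular inflammation, and subconjunctival hemorrhage". It also lists reactions seen with topical nepafenac, including foreign body sensation, pruritus, photophobia and tearing.

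**The concern.** Safety is half of the study objective (Section 3), and AE incidence and severity are a safety endpoint (Section 4.2.3). The product is a plug that Section 6.1.9 describes as larger than commercial silicone plugs, and it releases an NSAID. Its most informative tolerability events are the ones already foreseen. A definition that admits only unanticipated events leaves these without a clear instruction to record them.

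A site that follows 8.2.1 to the letter would record fewer events than a site that follows the spirit of 8.6.4. With up to three sites, the AE tables could then reflect reading habits as well as tolerability.

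The SAE definition in 8.2.2 is a subset of the AE definition, so the same word also reaches SAE reporting.

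**Working it through.** The plan gives no AE rate, and Section 10.5 says no sample size was calculated, so there is no figure to reproduce. The check is a reading of the text, followed by an illustration of scale.

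**Step 1: what 8.2.1 excludes.** The adjective most naturally governs sign, symptom and disease alike. An event the protocol itself foresees is not unanticipated, so on the literal text it is not an AE.

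**Step 2: whether another rule restores it.**

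- Section 8.7 lifts limits on severity and attribution. It does not mention expectedness, and it reuses the defined term.
- Section 8.6.4 requires forms for events that are anticipated and unlikely. It sets no threshold for unlikely.
- The open question put to subjects (7.2.1, 8.1) elicits problems. Whether an answer counts as an AE goes back to 8.2.1.

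Unanticipated events are thus covered by 8.2.1, and anticipated unlikely events by 8.6.4. Anticipated common events are expressly covered by neither.

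**Step 3: how the rest of the protocol uses the term.**

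- Section 7.5 expects no AEs of a new kind or intensity compared with published topical nepafenac experience. That treats the known reactions as AEs.
- Section 8.6.4 is about anticipated AEs and has an open list that includes corneal edema, iritis and treated IOP rises. It exempts wound burps and suture removal, which would hardly be needed if expected events were already out.
- Sections 8.6.3 and 8.7.3 treat unanticipated or unexpected events as a separate category with its own reporting.
- Section 10.4.4 defines treatment-emergent AEs by timing after plug insertion, with no expectedness limit.

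All four conflict with 8.2.1.

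**Step 4: serious events.** Section 8.2.2 defines an SAE as an AE that meets a seriousness criterion. The anticipated list in 8.6.4 includes endophthalmitis and retinal detachment. Taken literally, these fail 8.2.1 and hence 8.2.2, which is what triggers the 24-hour report in 8.7.2.

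**Step 5: scale, under an assumption.** Inputs are 50 N-PPDS subjects (Section 4.1) and the 0.1% label (Appendix 4, label section 6.1), which gives five ocular reactions at about 5–10% and eleven at about 1–5%. The assumption is that these rates carry over to the plug. Subject-events = reactions × 50 × rate.

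- All sixteen: 5 × 50 × 5–10% = 12.5–25, and 11 × 50 × 1–5% = 5.5–27.5. The total is 18–52.5.
- Seven are at least partly covered elsewhere. Corneal edema and treated IOP rises are listed in 8.6.4. Acuity is measured. Conjunctival edema, lid margin crusting and hyperemia fall within slit-lamp grading. Ocular pain is the primary endpoint.
- The remaining nine: 3 × 50 × 5–10% = 7.5–15, and 6 × 50 × 1–5% = 3–15. The total is 10.5–30.
- Section 2.3.1 gives 5–15% for the first group. With 15%, the upper end is 3 × 50 × 15% + 15 = 37.5.

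These are events whose recording depends on the reading. They are not an estimate of events lost.

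**Step 6: the between-arm test, under assumed rates.** With 50 and 25 subjects and two-sided α = 0.05, power ≈ Φ[(|pA − pP| − 1.96·SE0)/SE1]. SE0 uses the pooled proportion and SE1 the separate ones. If the same share of AE subjects is counted in both arms:

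| Assumed true any-AE rates (active vs placebo) | all counted | 75% | 50% | 25% |
|---|---|---|---|---|
| 40% vs 20% | 0.40 | 0.27 | 0.17 | 0.09 |
| 50% vs 20% | 0.73 | 0.52 | 0.31 | 0.14 |
| 60% vs 30% | 0.70 | 0.47 | 0.27 | 0.13 |

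For 50% vs 20%, all counted: pooled p = (25 + 5)/75 = 0.40, SE0 = √(0.24 × 0.06) = 0.120, SE1 = √(0.25/50 + 0.16/25) = 0.107, so Φ[(0.30 − 0.235)/0.107] = Φ(0.61) = 0.73.

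**The case against.** The strongest reply is that the protocol as a whole plainly means AEs to include expected events. Sections 7.5, 8.6.4, 8.7.3 and 10.4.4 all read that way, the question put to subjects is open, and an experienced site would record epiphora as an AE without a second thought. Much of this stands, and it rules out two stronger readings.

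A reader might infer that every AE count and the chi-square test rest on the narrow definition, so that all sixteen label reactions, 18–52.5 subject-events, go unrecorded. The documents do not support that. Section 8.6.4 puts some foreseen events on AE forms, and 10.4.4 counts by timing. Several reactions are also measured elsewhere: acuity, slit-lamp grades and pain, whose lowest non-zero grade overlaps with discomfort and foreign body sensation. Plug loss has its own CRF and log entries (6.1.7.4, 6.2). The label itself cautions against carrying rates from one drug's studies to another's.

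A reader might also infer bias between arms. None is shown: the same definition applies to both masked arms.

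What the reply does not do is point to a sentence that requires a form for an event that is anticipated and likely. It shows that the word in 8.2.1 is misplaced, but it does not remove it. Epiphora, pruritus, photophobia and foreign body sensation have no dedicated assessment in the schedule.

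**Conclusion.** Section 8.2.1 is wrong as written. It contradicts four other sections, and on its literal terms it leaves anticipated common reactions without a recording rule and anticipated serious events outside the SAE definition. The consequence is possible understatement of AE counts, or differences between sites, with a matching loss in the AE comparison.

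The documents do not fix the size of that loss. It runs from nothing, if every site records everything, up to the 10.5–30 subject-events in Step 5 (37.5 at the upper end with the Section 2.3.1 rate) for reactions with no other clear route, if topical rates apply to the plug. The power figures rest on assumed rates and an assumed share counted. They show only that the loss could matter in a study of 75.

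Visual acuity, slit-lamp, fundus, pain and rescue-use data are unaffected. This should be corrected, but it does not undermine the efficacy analysis.

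**What to change.** - **Section 8.2.1:** replace *unanticipated* with *untoward*, state that the event counts whether expected or not, and add *or device* after *medicinal product*.
- **Section 8.6.4:** delete *unlikely but*, so that every anticipated event gets an AE form. Keep the stated exemption for wound burps and suture removal.
- **Sections 8.6.3 and 8.7.3:** use expectedness only here, as a classifier for additional reporting.
- **Pain and cell/flare scores:** state how protocol-graded scores relate to AE recording. Without this, any pain or trace cells becomes an AE. Section 2.1 reports about 50% of vehicle and 80% of nepafenac 0.1% patients free of pain on Day 1, hence about 50% and 20% with pain, so the AE test would partly repeat the efficacy endpoint.
- **Section 10.4.4:** keep the separate presentation of events between consent and exposure. The revised definition should not start the clock at study treatment.

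The cost is a few sentences of amendment and somewhat more AE forms. No procedure or visit is added.
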